THE UNIVERSITY OF TEXAS

Protocol Abstract Page

The Pre-emptive Use of Recipient-Derived Autologous CMV-Specific Cytotoxic T Cells for CMV Reactivation After Allogeneic Stem Cell Transplantation.

2013-0620

Core Protocol Information

Study Chairman:	[name]
Department:	Stem Cell Transplantation and Cellular Therapy
[contact]
Unit:	423
Full Title:	The Pre-emptive Use of Recipient-Derived Autologous CMV-Specific Cytotoxic T Cells for CMV Reactivation After Allogeneic Stem Cell Transplantation.
Protocol Phase:	Phase II
Version Status:	Terminated 05/14/2019
Version:	11
Document Status:	Final

Abstract

Objectives:

Primary

1. To assess the efficacy of recipient-derived autologous cytomegalovirus (CMV)-specific cytotoxic T cells (CTLs) as a pre-emptive therapy for CMV reactivation after allogeneic hematopoietic stem cell transplantation (HSCT) from a CMV negative donor.
2. To assess the non-relapse mortality with the use of recipient-derived autologous cytomegalovirus (CMV)-specific cytotoxic T cells (CTLs) as a pre-emptive therapy for CMV reactivation after allogeneic hematopoietic stem cell transplantation (HSCT) from a CMV negative donor.

Secondary

1. To assess the safety of the pre-emptive use of recipient-derived autologous CMV- specific CTL as a pre-emptive therapy for CMV reactivation after HSCT.
2. To assess functionality and persistency of infused autologous CMV-specific CTLs.

Rationale: (Be as concise as possible)

CMV is a B-herpesvirus that is very common in humans and leads to asymptomatic infection followed by viral persistence and latency. CMV is still one of the major causes of infectious complications after HSCT, although several new prophylactic options for CMV infection/disease have been made available. Among the recipients of HSCT, CMV causes pneumonia, gastroenteritis, and less commonly retinitis and hepatitis. Because of the initial high mortality of CMV pneumonia (80-90%), transplant physicians have long sought strategies to reduce its morbidity and mortality. CMV also exhibits an immunosuppressive

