effect, which can lead to an increased susceptibility to invasive bacterial and fungal disease as well as graft versus host disease (GVHD) in selected clinical settings. Recent advances in diagnostic measures such as CMV antigenemia and polymerase chain reaction (PCR) and the introduction of effective antiviral agents have enabled sufficiently early detection of CMV to suppress reactivation and prevent subsequent development of CMV diseases (pre-emptive therapy).

The presence of CMV-specific T cell immunity has been reported to be an essential host factor in the control of infection and the recovery from CMV disease decades ago. However, restoration of T-cell immunity after HSCT is a slow process. The rebound of the thymus occurs late, particularly in adult patients, and the contribution of newly generated T cells during the first 6 months after transplantation may be negligible. Therefore, the initial protection against viruses has to come from the donor T cells co-infused with the graft or possibly from recipient T cells that have survived conditioning. This might leave some patients unprotected because no immunity is transferred when a patient receives a transplant of hematopoietic stem cells (HSCs) from a CMV-negative donor or umbilical cord blood (UCB) units that have T cells one log less than other donors and naive. Therefore, the use of adoptive immunotherapy with CMV-specific CTLs to restore the cellular immunity for CMV infections after HSCT has been investigated by many groups.

In HSCT, seropositive stem cell donors can usually serve as T cell donors and are available for T-cell donation. However, some seropositive donors may not consent, may be unavailable to provide T cells, or may not have enough antiviral memory T cells in their blood despite seropositivity. Furthermore, UCB recipients with delayed hematologic engraftment and immune reconstitution represent a unique group with high risk for viral infections but without the option of adoptive transfer of virus-specific CTL. Those groups of patients need to be investigated further for strategies that bypass the need to grow donor-derived CTL.

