- 4) Patients with T Cell ALL must be in complete remission and MRD negative (-) by flow cytometry and molecular studies.
- 5) Patients \geq 18 years of age.
- 6) Karnofsky greater than or equal to 80%.
- 7) CMV seropositive.
- 8) Donor is either matched related, matched unrelated, mismatched unrelated, or haploidentical. Cord blood recipients are also eligible.
- 9) Hgb greater than 10 g/L.
- 10) Patient or patient's legal representative, parent(s) or guardian able to provide written informed consent.
- 11) Negative pregnancy test in female patients of childbearing potential.
- 12) STEP 2: Eligibility at time of generating and infusing CMV-specific cytotoxic T cells (adoptive immunotherapy): CMV reactivation defined as CMV DNAemia \geq 137 copies/ml.
- 13) Evidence of neutrophil engraftment defined as the absolute neutrophil count (ANC) $> 0.5 \times 10^3$ /for 3 consecutive days.
- 14) Clinical status to allow tapering of steroids to less than 0.5 mg/kg/day prednisone or equivalent.
- 15) Negative pregnancy test in female patients of childbearing potential.

Exclusion:

- 1) STEP 1: Within 30 days of study entry: T cell leukemia or lymphoma.
- 2) CMV seronegative.
- 3) Positive for HIV, HBV, HCV, HTLV1 and/or HTLV2.
- 4) STEP 2: Eligibility at time of generating and infusing CMV-specific cytotoxic T cells (adoptive immunotherapy): Documented CMV end-organ disease.
- 5) Patients receiving ATG, or Campath within 28 days of CMV reactivation.
- 6) Patients with other uncontrolled infections. For bacterial infections, patients must be receiving definitive therapy and have no signs of progressing infection for 72 hours prior to generating CTLs. For fungal infections patients must be receiving definitive systemic anti-fungal therapy and have no signs of progressing infection for 1 week prior to generating CTLs. Progressing infection is defined as hemodynamic instability attributable to sepsis or new symptoms, worsening physical signs or radiographic findings attributable to infection. Persisting fever without other signs or symptoms will not be interpreted as progressing infection.

- 7) Patients who have received donor lymphocyte infusion (DLI) within 28 days.
- 8) Patients with active acute GVHD grades II-IV.
- 9) Active and uncontrolled relapse of malignancy.

Are patients <18 years of age eligible to participate in this study? Yes No

Studies that include children must meet the criteria for inclusion.

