http://www.fda.gov/ohrms/dockets/AC/04/briefing/4028B1_05_NIH-Inclusion%20of%20Children.doc
<http://www.hhs.gov/ohrp/policy/populations/children.html>

Studies that exclude children must have appropriate justification. Please select all that apply:

Phase II or III study with no Phase I data for the drug in pediatrics.

Please provide a letter from the Sponsor stating if a Phase I study planned for patients <18 years of age. (May include file attachment)

- This is a rare disease in pediatric patients
- Our Pediatric transplant program is very small
- Our sponsor does not allow pediatric patients to be included in this study.

Are participants >65 years of age eligible to participate in this study? Yes No

Are pregnant women eligible to participate in this study? Yes No

Will the recruitment population at M. D. Anderson include persons who are incarcerated at time of enrollment (e.g., prisoners) or likely to become incarcerated during the study?

Yes No

Disease Group:

Blood And Marrow Transplantation, Leukemia, Lymphoma

Treatment Agents/Devices/Interventions:

CMV-specific CTLs

Proposed Treatment/Study Plan:

Is treatment assignment randomized? Yes No

Is this a blinded or double-blinded study? Yes No

Collection of peripheral blood mononuclear cells (PBMC) for manufacturing of CTLs

After enrollment, PBMC will be collected via venipuncture.

Venipuncture: up to 500 mL one time at the MD Anderson Blood Bank. The product will be cryopreserved for future use to generate CMV-specific CTLs.

PBMCs will be stored for 3 years. If the PBMCs are not needed to generate CTLs, they will be discarded.

Allogeneic HSCT and follow-up

1. Patients will undergo allogeneic HSCT per institutional guidelines.
2. CMV reactivation will be monitored by checking CMV DNA level by polymerase chain reaction (PCR).

Manufacture of recipient derived autologous CMV specific CTLs under GMP conditions

1. After documentation of CMV reactivation, defined as CMV DNA load is equal to or greater than 137 copies/ml, cryopreserved PBMC product of eligible patients' defined under "Eligibility" will be used for generation of CMV-specific CTLs.

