Statistical Considerations:

Treatment and Primary Outcomes. This is a single-arm phase II trial of autologous virus specific CTLs for CMV reactivation in patients with hematologic malignancies (excluding T cell leukemia and lymphoma) undergoing CMV seronegative matched unrelated donor (MUD), mismatched unrelated or cord blood allogeneic stem cell transplant. Whole blood will be collected and frozen prior to transplant. After documentation of CMV reactivation, defined as CMV at a level ≥ 137 DNA copies/ml by PCR, autologous CMV-specific CTLs will be generated to be infused within 72 hours of CMV reactivation, if the patient has ANC engraftment, no acute GVHD or steroid administration ≤ 0.5 mg/kg dose. All outcomes will be recorded starting from the time of T-cell administration. While the dose of T-cells will vary depending on how many cells can be grown by ex vivo expansion after thawing and prior to administration, the maximum dose will be $10e5$ viable CD3+ T cells/kg. It is anticipated that 20-25 patients per year will be accrued and that approximately 2 patients per month will develop CMV reactivation and thus be eligible to receive autologous CTLs. A maximum of 36 patients will receive autologous CTLs. The two primary endpoints, starting at the time of autologous T-cell administration, will be $T =$ time to non-relapse mortality and $Y =$ [28-day success], where "success" is defined as follows. CMV will be evaluated weekly at 7, 14, 21 and 28 days using PCR. Treatment will be considered a success if the patient does not require initiation of CMV anti-viral therapy. Anti-viral therapy will be started if 1) End-organ disease is documented at any time point after CTL administration 2) Increase in CMV DNAemia $>50\%$ compared with baseline at any time point 3) Decrease in CMV DNAemia $<50\%$ compared with baseline at day 21 after CTL administration and 4) CMV DNAemia >5000 copies/ml at any time point.

Non-relapse mortality is defined as death because of causes other than relapse of the underlying hematological malignancy. Relapse of underlying hematological malignancy will be a competing event for non-relapse mortality. Time to non-relapse mortality is defined as time to non-relapse mortality from date

of stem cell transplantation.

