Sample Size. The effective sample size for evaluating CTL effects is the number of patients who suffer CMV reactivation, are eligible to receive CTLs, and actually receive CTLs, not the number enrolled and undergoing a transplant. In order to obtain a maximum of 36 patients who are treated with CTLs, assuming an accrual rate of 5 patients per month who receive a transplant and a 40% rate of patients with CMV who satisfy the entry criteria for receiving CTLs, it is expected that an effective accrual rate total of 2 patients per month will be enrolled, receive a transplant, and subsequently develop CMV. Due to the randomness of the treatable CMV subsample size, which is binomial in $q = .40$ and $n =$ number of patients initially enrolled and transplanted, up to 105 patients will be enrolled (21 months accrual) to ensure at least a 90% probability that there will be at least 36 patients with CMV. If $q = .50$, then up to 83 patients (17 months accrual) will be enrolled to ensure this same sample size with this reliability. The overall sample size of 36 will ensure that, if the trial is not stopped early and, for example, 18/36 patients achieve 28-day success, then a posterior 95% credible interval for p starting with a beta (.50,.50) prior would be .342 - .658, or approximately 34% to 66%.

The first three patients on protocol will be observed for at least 28 days for safety monitoring before more patients are enrolled in the study.

Statistical Models and Early Stopping Rules

Probability of 28-day Success. The Bayesian method of Thall and Sung will be used to monitor the $p =$ the probability of 28-day success. Assume that the number of 28-day successes $Y \sim \text{binomial}(p, 36)$ and that *a priori* $p \sim \text{beta}(.5, .5)$. The trial will be stopped early if $\text{Pr}(p > .50 \mid \text{data}) < 0.010$. Assuming a $\text{beta}(500, 500)$ prior for the standard response probability, and monitoring continuously, the trial will be stopped early if $[\# \text{ patients with 28-day success}] / [\# \text{ patients evaluated for 28-day success}]$ is less than or equal to $0/5, 1/9, 2/12, 3/15, 4/18, 5/21, 6/24, 7/26, 8/29, 9/31, \text{ or } 10/34$.

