Operating Characteristics. The design's operating characteristics, with these two early stopping rules both implemented, are given below in Table 7. Due to the lack of computer software to evaluate the two monitoring rules together, (i) it is not possible to obtain achieved sample size distributions, and moreover (ii) it was necessary to compute the overall early stopping probability, given in the last column of Table 1, under the simplifying assumption that p and m are independent parameters, which of course is not true. However, denoting $Sp = [\text{stop due to the rule for } p]$ and $Sm = [\text{stop due to the rule for } m]$, since $\text{Pr}(Sp) = \text{Pr}(Sp | Sm)\text{Pr}(Sm) + \text{Pr}(Sp | \text{not } Sm)(1 - \text{Pr}(Sm))$, if p and m are positively associated, which seems a reasonable assumption, then $\text{Pr}(Sp | Sm) > \text{Pr}(Sp)$ and $\text{Pr}(Sp | \text{not } Sm) < \text{Pr}(Sp)$, so it is unclear precisely how actual association between the two parameters will affect the joint behavior of the two rules. If appropriate computer software were available, this issue could be explored more precisely.

Secondary Outcomes. Additional outcomes will include overall survival time, disease-free survival time, relapse rate, secondary graft failure, and graft-versus-host disease as an ordinal outcome. Each of these variables which will be analyzed as a function of patient covariates using standard statistical methods, including Bayesian survival regression analysis and ordinal regression. Unadjusted event time distributions will be estimated using the Kaplan-Meier method.

Table 7. Operating characteristics of the two early stopping rules.

Scenario	P(Response)	P(Death < 6 Months)	P(Stop Early due to Response Rule)	P(Stop Early due to Death Rule)	P(Stop Early: Overall)
1	0.50	0.45	0.070	0.100	0.163
2	0.30	0.45	0.681	0.100	0.712
3	0.50	0.60	0.070	0.374	0.418
4	0.30	0.60	0.681	0.374	0.800
5	0.50	0.65	0.070	0.648	0.672
6	0.30	0.65	0.681	0.648	0.888

Stopping Rules

The Bayesian decision cut-off for the treatment failure time event is to **STOP** accrual to the trial if $\text{Prob}(\text{median} > 6.96 | \text{data}) < 0.0717$.

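### The primary objectives concern CMV-negative donors, but eligibility sets no donor CMV criterion, so the 28-day success rule and the 36-patient interval need not describe the population in objective 1

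*Combined protocol and SAP*

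**What the plan says.** - **Objectives, Primary.** Both the efficacy and the non-relapse mortality objective concern "stem cell transplantation (HSCT) from a CMV negative donor".
- **Eligibility, inclusion criterion 8.** "Donor is either matched related, matched unrelated, mismatched unrelated, or haploidentical. Cord blood recipients are also eligible". The list is presented as complete. Its CMV serostatus criteria (inclusion 7, exclusion 2) concern the patient. Neither Step 1 nor Step 2 sets a donor CMV status.
- **Statistical Considerations, Treatment and Primary Outcomes.** The trial is described in patients "undergoing CMV seronegative matched unrelated donor (MUD), mismatched unrelated or cord blood allogeneic stem cell transplant". Matched related and haploidentical donors are not named, and it is unclear whether the word seronegative covers all three graft types or only the first.
- **Manufacture of CTLs.** Cells are made from the stored product of patients who meet the eligibility list: "eligible patients' defined under 'Eligibility' will be used for generation of CMV-specific CTLs".
- **Sample Size.** The effective sample is "the number of patients who suffer CMV reactivation, are eligible to receive CTLs, and actually receive CTLs".
- **Secondary Outcomes.** The only covariate analysis is planned here, for secondary outcomes: "Each of these variables which will be analyzed as a function of patient covariates using standard statistical methods".

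**The concern.** Three parts of the plan name three different donor populations, and the broadest one decides who is treated. Followed as written, the trial can produce a 28-day success estimate, and a decision under the rule for p, in a donor mix that objective 1 does not name. The non-relapse mortality estimate for objective 2 would come from the same mix.

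The Rationale gives a reason why serostatus might matter: "no immunity is transferred when a patient receives a transplant of hematopoietic stem cells (HSCs) from a CMV-negative donor". If that means lower success in recipients of CMV-negative donors, pooling them with others would mask failure in the group the objective is about. The Rationale does not settle the matter, though. Every treated patient has already reactivated, and nothing in the documents shows a difference between donor groups after that selection. Nor does it fix the intended population. It also discusses seropositive donors who cannot supply T cells, and it presents seronegative donors and cord blood as the main need rather than the only one.

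**Working it through.** **Inputs from the plan.** Beta(.5,.5) prior for p; stopping boundaries 0/5, 1/9, 2/12, 3/15, 4/18, 5/21, 6/24, 7/26, 8/29, 9/31, 10/34; at most 36 treated; q = 0.40, or 0.50 as the alternative; Table 7.

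**Assumed, because the documents give no value.** The share s of treated patients outside the target group (CMV-negative donor or cord blood), and success by donor group.

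**1. The plan's own figures.**
- 18/36: the posterior is beta(18.5, 18.5), with 95% interval 0.342 to 0.658, as stated.
- An exact patient-by-patient recursion over the stated boundaries, to n = 36, gives P(stop) = 0.681 at p = 0.30 and 0.070 at p = 0.50. Both match Table 7.
- The smallest n with binomial P(at least 36) of 0.90 or more is 105 at q = 0.40 (P = 0.903) and 83 at q = 0.50 (P = 0.906), as stated.

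**2. Response rule in a mixed population.** If each treated patient is independently target or other, the rule sees pooled p = 0.30 + s × (p_other − 0.30). For example, s = 0.25 and p_other = 0.50 give 0.30 + 0.25 × 0.20 = 0.35.

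P(stop by the response rule), target success 0.30:

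| Success in others | s = 10% | s = 25% | s = 50% |
|---|---|---|---|
| 0.30 (no gap) | 0.681 | 0.681 | 0.681 |
| 0.40 | 0.639 | 0.574 | 0.466 |
| 0.50 | 0.596 | 0.466 | 0.276 |

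In the opposite direction (target 0.50, others 0.30), pooled p is 0.48, 0.45 and 0.40, and P(stop) rises from 0.070 to 0.095, 0.145 and 0.276.

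**3. Precision in the target group at 50% success.** The interval is 0.310 to 0.690 at 12/24 and 0.284 to 0.716 at 9/18. The width grows from 0.316 at 18/36 to 0.433 at 9/18. This loss needs no gap between the groups.

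**4. Restricting the rule to target patients within the cap of 36.** At p = 0.30, P(stop) is 0.530 with 24 countable patients and 0.447 with 18, against 0.681 with 36. These count a stop at the last countable patient; without that final look they are 0.492 and 0.394.

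**5. Enrolment needed for 36 treated target patients under the broad list.** Effective q is the target share of those enrolled times the treatable fraction in that group. A fraction of 0.50 is the Sample Size section's alternative ("then up to 83 patients (17 months accrual) will be enrolled to ensure this same sample size"), applied here to the target group by assumption.

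| Target share | Fraction 0.40: effective q, n | Fraction 0.50: effective q, n |
|---|---|---|
| 75% | 0.30, 142 | 0.375, 113 |
| 50% | 0.20, 215 | 0.25, 171 |
| 25% | 0.10, 435 | 0.125, 347 |

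With 105 enrolled, the chance of at least 36 treated target patients is 0.196 (75% share) or 0.0004 (50% share) at fraction 0.40, and 0.782 or 0.021 at fraction 0.50.

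**The case against.** The strongest reply is that the statistical section already states its population, and that the rule for p and the 36-patient interval inherit it. No sentence says that recipients of CMV-positive donors count. This is a fair reading of intent, but the description enforces nothing. Manufacture is tied to the eligibility list, under which a recipient of a seropositive donor can be treated without any deviation. The description also disagrees with criterion 8 on donor types, so the texts need reconciling either way.

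A second reply is that no harm is shown: donor mix and success rates are assumed, and the Rationale speaks of immunity carried by the graft, not of response to infused recipient cells. This stands as far as size is concerned. It is also true that the error could run the other way, with extra stopping if others do worse; that case is given above. The documents suggest a direction but do not establish it.

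A third reply is that the broad list may be deliberate. It may be. In that case the primary objectives and the statistical description are what must change.

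Finally, the accrual cost depends on the Sample Size section's 5 transplants per month applying to the broad list. If that rate already describes the narrower population, a donor criterion adds no time. The figure of 2 per month elsewhere is consistent with treated patients (5 × 0.40 = 2).

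**Conclusion.** The concern holds and should be fixed. That the objectives, criterion 8 and the statistical section disagree on donors is certain from the text, and nothing later in the plan repairs it.

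The numerical consequence is unknown. With no difference between donor groups, Table 7 stands for the response rule. If target success is 0.30 and that in others is 0.40 to 0.50, with 10% to 50% others, P(stop by the response rule) lies between 0.639 and 0.276 instead of 0.681. These figures rest on assumed shares and rates and on treated patients being an independent mix. The loss of precision for the objective 1 population follows from its share alone. No effect on the mortality rule was computed.

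**What to change.** Make the primary objectives, inclusion criterion 8 and the opening of Statistical Considerations name one population. The choice is the sponsor's.

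**Option A: CMV-negative donors are intended.** Add a Step 1 criterion that the donor is CMV seronegative or the graft is cord blood. Align the donor types in criterion 8 and the statistical section, without dropping CMV-negative related or haploidentical donors merely because the latter omits them. The response-rule column of Table 7, n = 36 and the stated interval then apply to the target group, and 105 enrolled holds if q = 0.40 applies there. The cost is one eligibility line, some wording and possibly slower accrual. If 5 per month refers to the broad list, 105 takes 105/3.75 = 28 months at 75% target patients or 105/2.5 = 42 months at 50%, instead of 21.

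**Option B: the broad list is intended.** Restate the primary objectives and the statistical description for all CMV-seropositive recipients, and keep the rule for p on all 36. Record donor CMV serostatus, and report 28-day success and non-relapse mortality by serostatus with the wider subgroup intervals. The cost is wording, one table and a less precise estimate for recipients of CMV-negative donors.

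Do not apply the rule for p to a subset within the cap of 36 without restating Table 7. Keeping the broad list while requiring 36 treated target patients is costly, at 113 to 435 enrolled under the assumptions above. The version is marked as terminated, so any report of objective 1 should also state the donor serostatus of the treated patients.

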The protective role of recipient T cells after transplantation was not investigated in detail until recently because most transplantation protocols eradicate recipient T cells through a combination of the conditioning chemotherapy and an allogeneic effect of the graft. The notion that recipient T cells could survive even early after transplantation was supported by data from pediatric patient population undergoing UCB transplantation and showed that antigen-specific T lymphocytes of recipient origin were detected in patients receiving a transplant with a related donor, after a chemotherapy-based conditioning regimen, and who did not have GVHD(27). Recently, Chalandon et al showed when a T-cell depletion protocol was used that allowed recipient T cells to repopulate the T-cell compartment, the T cells maintained their function even after conditioning that includes total body irradiation. Furthermore, T cells appeared to protect the patient from CMV-related complications. These data support the notion to investigate the use of recipient-derived autologous CTLs for CMV reactivation after allogeneic HSCT especially for patients without the option to use donor-derived CTLs. Recently, Meij et al. showed the feasibility of generating patient-derived autologous CMV specific CTLs using IFN γ -capture system.

In conclusion, alternative strategies to provide safe and effective adoptive therapy for CMV reactivation after HSCT are needed especially in patients with CMV seronegative donors or following the use of UCB where there is no memory T cell response to CMV.

In this study, we will use this original and novel approach of infusing recipient-derived autologous CMV-specific CTLs for the treatment of CMV reactivation following HSCT in CMV seropositive patients.

Eligibility: (List All Criteria)

Inclusion:

- 1) STEP 1: Within 30 days of study entry: Patients with a history of bone marrow disorders including hematological malignancies and aplastic anemia, Myelodysplastic Syndrome (MDS) and Myeloproliferative disorder (MPD) planning to undergo allogeneic HSCT with reduced intensity or myeloablative conditioning regimens.

- 2) Disease status must be complete remission by standard criteria for Lymphoma and Acute Leukemia patients.
- 3) Patients with Myelodysplastic Syndrome (MDS) and Myeloproliferative Disorder (MPD) must have <5% blasts in the bone marrow.

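### Inclusion 9 sets the hemoglobin limit at 10 g/L, which is 1 g/dL and excludes effectively no one; g/dL is almost certainly the unit meant.

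*Combined protocol and SAP*

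**What the plan says.** The Eligibility section has two steps. STEP 1 governs study entry before transplant and runs from Inclusion 1 to Inclusion 11; STEP 2 starts at Inclusion 12 and governs CTL generation and infusion. The hemoglobin rule, Inclusion 9, belongs to STEP 1: "Hgb greater than 10 g/L".

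Three other places bear on how to read it:

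- **Population.** Inclusion 1 opens STEP 1 with "Within 30 days of study entry: Patients with a history of bone marrow disorders including hematological malignancies and aplastic anemia", and goes on to name MDS and myeloproliferative disorder.
- **Performance status.** Inclusion 6 requires "Karnofsky greater than or equal to 80" percent.
- **Blood collection.** The section on collecting peripheral blood mononuclear cells says "After enrollment, PBMC will be collected via venipuncture" and gives the amount as "Venipuncture: up to 500 mL one time at the MD Anderson Blood Bank". Statistical Considerations (Treatment and Primary Outcomes) places this before transplant: "Whole blood will be collected and frozen prior to transplant".

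No other part of the supplied text gives, restates or corrects a hemoglobin limit.

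**The concern.** A threshold of 10 is familiar for hemoglobin in g/dL and makes no sense in g/L. If the unit is taken at face value, an operative entry rule does nothing, and it does so in a population where anemia is to be expected.

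Two things are at stake, both modest. First, patients have up to 500 mL drawn after enrollment, and Inclusion 9 is the only hemoglobin threshold in the supplied text that stands before that draw. Second, eligibility cannot be audited cleanly: a patient at 8 g/dL complies with the printed rule but would be an eligibility deviation under the rule that was probably intended.

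**Working it through.** This is a unit conversion. The limit is a stated threshold, not a derived figure, so there is no calculation of the plan's to reproduce.

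**Inputs**

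- Printed limit: above 10 g/L (Inclusion 9).
- Karnofsky of at least 80% (Inclusion 6).
- Assumed intended limit: above 10 g/dL. This is an inference; the documents do not state it.

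**Conversion**

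1 L = 10 dL, so a value in g/L divided by 10 gives g/dL.

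- Printed limit: 10 / 10 = 1 g/dL.
- Assumed intended limit: 10 × 10 = 100 g/L.
- Ratio: 100 / 10 = 10. The printed limit is ten times too low.

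**What each reading does**

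| Hemoglobin | As printed (> 10 g/L) | With the unit as g/dL (> 10 g/dL) |
|---|---|---|
| ≤ 1 g/dL (≤ 10 g/L) | fails | fails |
| > 1 to 10 g/dL (> 10 to 100 g/L) | passes | fails |
| > 10 g/dL (> 100 g/L) | passes | passes |

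Only the middle row differs. A patient at 8 g/dL (8 × 10 = 80 g/L) falls in it.

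**Does the printed rule exclude anyone?** It excludes only patients at or below 1 g/dL. As general clinical knowledge, not a figure from the documents, that level is at the edge of survival. No such patient would have a Karnofsky score of 80% or more, so Inclusion 6 has already removed everyone the printed Inclusion 9 could remove.

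**Could another unit fit?** If the number 10 is kept, the other common unit is mmol/L (monomer). There 10 would be about 16 g/dL, an implausible floor for patients with marrow disorders. That leaves g/dL.

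**The case against.** The strongest objection is that the error may not be in the plan at all. It comes down to one letter in text that a program read from PDF, and the same list is damaged nearby: Inclusion 13 has lost the unit after its slash in the neutrophil criterion. This stands in part. Inclusion 13 was set as a formula and has a visible gap, whereas Inclusion 9 is plain text with a complete, well-formed unit. A lost letter is possible but not shown, and it caps confidence at medium.

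Further objections, and what remains of each:

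- **A fuller protocol may exist.** The document is headed as an abstract page, its tables start at Table 4, and it refers to a Table 1 that is not present. The statement that no other hemoglobin limit exists therefore covers the supplied text only. The eligibility section does, however, present itself as a list of all criteria, so Inclusion 9 is operative as it stands.
- **The value of 10 g/dL is inferred.** This stands. The documents contain no second hemoglobin value and no rationale. In a population that includes aplastic anemia and MDS, a floor of 10 g/dL would be a real restriction, so the investigator should confirm it.
- **The link to the blood draw is conjecture.** The plan does not say that the limit was set for the draw, and the Blood Bank may apply limits of its own. Nothing shows that any patient would be drawn at an unsafe level. The draw is a reason to get the rule right, not evidence of harm.
- **Little practical effect.** This is a single-center study, the literal reading is absurd enough to signal its own error, and staff would probably read g/dL. This limits the severity. It does not make the text correct, because a written entry rule should not depend on readers correcting it silently.
- **The version is marked as terminated on 05/14/2019.** A correction would be retrospective, which lowers its value for this trial but not for any reuse of the criteria.

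**Conclusion.** The concern holds. As printed, Inclusion 9 sets a limit of 1 g/dL, ten times below the assumed intended 10 g/dL, and beside the Karnofsky requirement it excludes effectively no one. The readings differ for all patients above 1 and up to 10 g/dL, a group whose size the documents do not allow to be estimated.

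The conclusion rests on two assumptions: that the source document also prints g/L, and that the number 10 is right and only the unit is wrong. The first can be settled by looking at the source page; if it reads g/dL, the point falls. The second needs the investigator.

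The severity is low and confidence is medium. No sample size, stopping rule or analysis depends on this criterion.

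**What to change.** Check the source page first. If it reads g/L, change the unit in Inclusion 9 to g/dL, so that the limit is above 10 g/dL (equivalently, above 100 g/L), with the investigator confirming that 10 g/dL is the intended value.

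The cost is one unit in the eligibility list, with no change to the design or the analysis. Because this version is terminated, the practical form is a correction or clarification on file, with the corrected unit carried into any later protocol that reuses these criteria.
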